The present study aims to compare the clinical outcomes of NPWT combined with HPTC skin substitute versus NPWT alone in patients with full-thickness wounds, using a randomized controlled design, to provide robust evidence for clinical decision-making in advanced wound care. Our hypothesis is that the combination therapy will result in significantly greater wound area reduction, faster closure, improved scar quality, and better patient-reported pain outcomes, without increasing adverse events.

MATERIALS AND METHODS

This was a prospective, randomized, open-label, parallel-group clinical trial conducted at the Department of Plastic, Reconstructive, and Aesthetic Surgery, Adichunchanagiri Institute of Medical Sciences (AIMS), Karnataka, India. The study compared the efficacy of Negative Pressure Wound Therapy (NPWT) combined with High Purity Type-I Collagen (HPTC) skin substitute versus NPWT alone in the management of full-thickness wounds. Patient recruitment occurred between March 2025, and July 2025. The anticipated follow-up continued until August 2025, with each participant observed for a total of seven weeks (six weeks of intervention plus one-week follow-up). The trial was registered prospectively with **ClinicalTrials.gov (ID: NCT06873867)** and approved by the Institutional Ethics Committee (**Approval No: AIMS/IEC/013/2025**). The study adhered to the principles of the Declaration of Helsinki and Good Clinical Practice guidelines. All participants provided written informed consent prior to enrollment after comprehensive explanation of study procedures, risks, and benefits. Patient confidentiality was maintained throughout the study period.

Patients aged 18-80 years with full-thickness wounds (wound depth extending through dermis into subcutaneous tissue), including traumatic, post-surgical dehiscence, burns ulcers, pressure ulcers, DFUs, or VLUs, wound size $>20 \text{ cm}^2$ and $<75 \text{ cm}^2$, with adequate vascular supply to the wound site, ability to comply with treatment protocol and follow-up visits, and provided written informed consent were eligible.

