Exclusion criteria included active infection or osteomyelitis requiring systemic antibiotics, active malignancy at wound site, immunosuppression, uncontrolled diabetes ($\text{HbA1c} > 9\%$), on systemic corticosteroids, patients on anticoagulation therapy with $\text{INR} > 3.0$ used advanced wound care products within the last 30 days, autoimmune or connective tissue disorders or allergy to bovine collagen.

Sample Size - Sample size calculation was based on the primary outcome of wound area reduction. Assuming a mean difference of 30% in wound area reduction between groups, with a standard deviation of 20%, power of 80%, and alpha of 0.05, a minimum of 47 patients per group was required. Accounting for 10% dropout rate, at 52 patients per group, with a total of 104 patients were recruited. This calculation was informed by effect sizes reported in previous HPTC RCTs in diabetic foot, venous leg and pressure ulcers, which demonstrated mean differences of 10–15% in wound healing outcomes. [6,7].

Randomization and Blinding - Participants were randomized 1:1 into two treatment groups using a computer-generated randomization sequence with block sizes of 4, 6, and 8. Patients were assigned to either: - Group A: NPWT + HPTC or Group B: NPWT alone.

Randomization was stratified by wound etiology. Allocation concealment was maintained using sequentially numbered, opaque, sealed envelopes prepared by a research assistant not involved in patient care or outcome assessment. Due to the nature of the intervention, complete blinding was not feasible; however, outcome assessors, pathologists, and data analysts were blinded to treatment allocation.

Intervention Protocol

Group A (NPWT + HPTC) - The wound was first debrided to remove necrotic tissue and ensure a viable wound bed. A sheet of High Purity Type-I Collagen skin substitute (Helicoll[®]) was applied to completely cover the wound surface. This was followed by a non-adherent porous dressing layer. NPWT was then applied using polyurethane foam at ~125 mmHg intermittent pressure (10 minutes on, 2 minutes off) for 5–7 days. The dressing was changed as per SOC thereafter, with repeat application of HPTC and NPWT as needed.

Group B (NPWT alone) - Following debridement, a non-adherent porous dressing was applied directly over the wound. NPWT was then initiated with the same parameters (polyurethane foam, ~125 mmHg, intermittent mode) and followed by SOC dressing. NPWT was reapplied if required.

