		Very high activity with extensive matrix deposition	3
Capillary density	Evaluated using CD31 staining, counted as vessels per mm^2 of tissue		
Inflammatory response	Graded semi-quantitatively (0–3 scale)	Minimal inflammatory infiltrate	0
		Mild chronic inflammation	1
		Moderate mixed inflammation	2
		Severe acute inflammation	3
Collagen deposition	Assessed using Masson's trichrome staining (0–3 scale)	Minimal collagen matrix	0
		Loose, immature collagen	1
		Moderate organized collagen	2
		Dense, mature collagen architecture	3

Table 2: Vancouver Scar Scale

Parameter	Score
Vascularity	0–3
Normal	0
Pink	1
Red	2
Purple	3
Pigmentation	0–2
Normal (matches surrounding skin)	0
Hypopigmentation	1
Hyperpigmentation	2
Pliability	0–5
Normal	0
Supple (flexible with minimal resistance)	1
Yielding (gives way to pressure)	2
Firm (resists movement)	3
Banding / rope-like tissue (may blanch on extension)	4
Contracture (permanent shortening producing deformity)	5
Height / Thickness	0–3
Flat / normal	0
< 2 mm	1
2–5 mm	2
> 5 mm	3

Parameter	Score
Total Scar Score (Higher scores indicate greater scar severity)	0-13

Data Collection and Measurement

Wound photographs were obtained using standardized digital photography with measurement grids. Standardized wound assessments were performed including digital photography, wound measurements using validated techniques, and clinical evaluations. Wound area was calculated by tracing the wound margin onto a sterile transparent film and photographing with a scale reference. Histological evaluation was performed on wound biopsies with stains as mentioned in Table 1. Pain assessments (Visual Analogue Scale) and quality of life score were completed at baseline, every week thereafter for 7 weeks.

Statistical Analysis

All data were analyzed using SPSS version 26.0 (IBM Corporation, Armonk, NY). Continuous variables were expressed as mean \pm standard deviation and compared using independent t-tests or Mann–Whitney U tests where appropriate. Categorical variables were expressed as frequencies and percentages, compared using chi-square or Fisher’s exact test. Repeated measures ANOVA was employed for longitudinal outcome analysis. Time-to-event outcomes were analyzed using Kaplan-Meier survival analysis with log-rank tests.

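### Randomisation is stratified by wound etiology, but no named analysis is stated to use etiology; if etiology is prognostic, the unadjusted tests are conservative and have less power than adjusted ones.

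*Combined protocol and SAP*

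**What the plan says.** Under Randomization and Blinding: "Participants were randomized 1:1 into two treatment groups using a computer-generated randomization sequence with block sizes of 4, 6, and 8", and then "Randomization was stratified by wound etiology". The strata are not listed. The eligibility paragraph of Materials and Methods admits six kinds of wound, "including traumatic, post-surgical dehiscence, burns ulcers, pressure ulcers, DFUs, or VLUs".

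The Statistical Analysis section says continuous variables were "compared using independent t-tests or Mann–Whitney U tests where appropriate", and categorical variables by chi-square or Fisher's exact test. It adds "Repeated measures ANOVA was employed for longitudinal outcome analysis" and "Time-to-event outcomes were analyzed using Kaplan-Meier survival analysis with log-rank tests". No test is described as stratified by, or adjusted for, etiology, and no factors are given for the repeated measures ANOVA. The document mentions no ANCOVA, regression model, stratified log-rank test or stratified test of proportions.

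The Sample Size paragraph assumes a difference of 30% with SD 20%, but refers to earlier trials "which demonstrated mean differences of 10–15% in wound healing outcomes".

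**The concern.** Blocking within etiology makes the arms nearly equal in etiology mix. Any variation in healing between etiologies then largely cancels from the difference between arms. A two-sample t-test does not know this and leaves that variation in its error term. If etiology is prognostic, the reported standard error exceeds the true one, the confidence interval is too wide and the test rejects too seldom under the null. If etiology is not prognostic, there is no such problem.

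Etiology is plausibly prognostic here. It is the only stratification factor named, the eligible wounds run from trauma to venous and diabetic ulcers, and the standardised care differs by wound type. At stake is efficiency: part of what stratification bought goes unused in the primary comparison and in both closure outcomes.

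Baseline wound area is a different matter. It was not a stratification factor, so leaving it out keeps the standard error valid and only forgoes possible precision. That gain is uncertain because the outcome is already a percentage.

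**Working it through.** **Inputs from the plan.** Difference 30, SD 20, power 80%, alpha 0.05 (taken as two-sided), 47 per group, 52 per group after 10% dropout, 1:1 allocation in blocks of 4, 6 and 8 within etiology.

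**Assumed, because the plan does not say.** Six strata (from the eligibility list) and a share R² of outcome variance explained by etiology from 0 to 0.3.

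**The plan's own sample size.** n = 2(1.960 + 0.842)² × (20/30)² = 2 × 7.849 × 0.444 = 6.98, so 7 per group (8 to 9 with the t distribution), not 47. Solving for the difference that 47 per group detects: 20 × √(2 × 7.849/47) = 11.6 points. That is a separate problem. It matters here because it places the design's effective target inside the cited 10–15% range.

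**Formula check.** The t-test's standard error is SE = 20 × √(2/47) = 4.13. With balanced strata the true value is SE × √(1 − R²).

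- Type I error = 2[1 − Φ(1.96/√(1 − R²))], which gives 5.0%, 3.9%, 2.8% and 1.9% at R² = 0, 0.1, 0.2 and 0.3.
- Unadjusted power = Φ((δ/SE − 1.96)/√(1 − R²)). At δ = 10, δ/SE = 2.424, giving 67.9%, 68.8%, 69.8% and 71.0%.
- Adjusted power = Φ(δ/(SE√(1 − R²)) − 1.96). At δ = 10 this gives 67.9%, 72.4%, 77.3% and 82.6%.

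**Simulation.** 20,000 trials per R²: 104 randomised in blocks within six equal strata, a random 94 analysed, total SD 20. The adjusted analysis is a linear model with stratum terms. The mean standard error reported by the t-test was 4.12 throughout.

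| | R² = 0 | 0.1 | 0.2 | 0.3 |
|---|---|---|---|---|
| True SD of unadjusted difference | 4.15 | 3.98 | 3.76 | 3.58 |
| Type I error, unadjusted | 5.1% | 4.2% | 3.1% | 2.3% |
| Type I error, adjusted | 5.0% | 5.2% | 4.9% | 4.9% |
| 95% CI half-width, unadjusted | 8.2 | 8.2 | 8.2 | 8.2 |
| 95% CI half-width, adjusted | 8.2 | 7.8 | 7.4 | 6.9 |
| Power at 10 points, unadjusted / adjusted | 66.4 / 66.2% | 67.4 / 70.8% | 68.5 / 76.0% | 69.1 / 81.6% |
| Power at 12 points | 81.5 / 81.3% | 82.8 / 85.1% | 84.3 / 89.5% | 85.8 / 93.0% |
| Power at 15 points | 94.7 / 94.5% | 95.3 / 96.1% | 96.3 / 98.1% | 97.2 / 99.2% |
| Power at 30 points | 100 / 100% | 100 / 100% | 100 / 100% | 100 / 100% |

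A separate simulation of 94 patients without dropout gave unadjusted type I error of 4.8%, 3.8%, 2.7% and 2.5%. Unequal strata (35/25/15/12/8/5%) gave 5.0%, 4.2%, 3.5% and 2.5%.

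**Closure outcomes.** All rates here are assumed: 94 patients, hazard ratio 2, weekly assessment to day 49, mean control closure about 40%, 3,000 trials.

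| Control closure across etiologies | Log-rank / stratified | Chi-square / Cochran-Mantel-Haenszel |
|---|---|---|
| 40% in all | 67.6 / 65.9% | 65.3 / 65.0% |
| 20% to 64% | 59.3 / 66.0% | 55.0 / 60.2% |
| 8% to 83% (extreme) | 41.9 / 63.4% | 36.2 / 53.2% |

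In the 20% to 64% case both unstratified tests had type I error of 4.3%; in the extreme case, about 2%. A second set-up (104 patients, hazard ratio 1.8, log-hazards spread ±0.5 or ±1.0 across etiologies) agreed: unstratified log-rank type I error was 4.2% or 2.5%, and power was 67% against 70%, or 54% against 69% stratified.

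**The case against.** The best reply is that nothing here threatens validity. The estimate is unbiased, type I error is at or below 5%, and a significant result would stand. Nor does the unadjusted test fall below its planned power: at a fixed total SD its power rises slightly with R² (66.4% to 69.1% at 10 points). The loss exists only relative to an adjusted analysis. Within the cited 10–15% range, unadjusted power is below 80% only near 10 points. R², the strata and every closure rate are assumed, and the R² range includes zero. The primary outcome spans several weeks and may be meant for the repeated measures ANOVA, which could carry etiology as a factor. Neither that model nor the Mann–Whitney test was simulated. Finally, the mismatch in the sample size calculation is the larger power problem.

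Most of this stands and sets the bounds of the point. It does not remove it. An ANOVA whose factors are not stated cannot be credited with an etiology term, and the t-test, log-rank and chi-square tests have no place for one as described. Even where power is about 100%, the unadjusted interval is wider than it needs to be if etiology is prognostic.

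**Conclusion.** The concern holds. The plan stratifies by etiology and states no analysis that uses it. If etiology explains 10% to 30% of the variance in percentage area reduction, the nominal 5% t-test runs at about 4.2% to 2.3%, and its 95% interval has a half-width of 8.2 points where 7.8 to 6.9 would be valid. Adjustment would add 3.4 to 12.5 percentage points of power at a true difference of 10, 2.3 to 7.2 at 12, 0.8 to 2.0 at 15 and none at 30. The closure tests behave in the same way.

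These sizes rest on the assumed R² range, six strata, SD 20 and the t-test as the primary comparison; for closure they also rest on the assumed rates and hazard ratios. The omission and the direction of its effect are firm, but the size is conditional. It should be changed because the remedy is nearly free, although it does not put a positive finding in doubt.

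**What to change.** - **Primary outcome:** a linear or mixed model of percentage area reduction with treatment and etiology stratum. Baseline area may be added as an optional precision covariate.
- **Time to closure:** a log-rank test stratified by etiology.
- **Closure proportion:** a Cochran-Mantel-Haenszel test by etiology.
- **Pain and EQ-5D change:** include etiology. Adjusting for the baseline score as well is sensible, but is a precision choice separate from the stratification.
- **Specification:** list the etiology categories used as strata, state the factors in the repeated measures ANOVA, and give a rule for merging very small strata that is fixed without reference to treatment results.

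The cost is low. Etiology was recorded for randomisation, and SPSS 26 runs these analyses. If etiology is not prognostic, the linear model loses less than 1 percentage point of power and the stratified log-rank test up to about 2.

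Timing limits what can be claimed. The document is dated November 09, 2025, and says "The anticipated follow-up continued until August 2025". If outcome data are already unblinded, keep the planned unadjusted tests, report the etiology-adjusted analyses beside them and label those as added later.

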All patients received standardized wound care including sharp debridement as needed to remove non-viable tissue, infection control with topical antimicrobials when indicated, pressure redistribution and offloading as appropriate, nutritional assessment and optimization, glycemic control for diabetic patients, compression therapy for venous ulcers and pressure offloading for wounds when appropriate. Patient education on wound care was given.

Outcome Measures

The primary outcome of the study was percentage wound area reduction from week 1 through week 6 plus 1 week follow up, measured via digital photography. Measurements were performed by trained personnel blinded to treatment allocation.

Secondary outcomes included time to complete wound closure (in days) within 7 weeks, proportion of patients achieving complete closure by week 7, histological vascularity infiltration, between baseline (Day 0) and Day 5 biopsies, mean number of applications of the skin substitute required, incidence of adverse events (infection, allergic reaction, bleeding,

maceration), pain score change using a 0–10 Visual Analog Scale (VAS) from baseline to week 6, and scar quality assessed at week 7 using the Manchester Scar Scale (MSS).

Complete wound closure is defined as 100% epithelialization. Histopathological assessment included taking punch biopsies (2 mm) from the wound edge at baseline and day 5 post-intervention under local anesthesia (2% lidocaine without epinephrine). Fixation in 10% neutral buffered formalin for 24 hours, processing through graded alcohol and paraffin embedding, and serial sectioning at 4 μ m thickness was done. Samples were processed using standard histological techniques and stained with hematoxylin and eosin (H&E), Masson's trichrome, CD31 immunohistochemistry, and α -SMA immunohistochemistry. Assessment parameters included vascular infiltration (0-3 scale), neo-epithelialization (0-3 scale), fibroblast activity (0-3 scale), capillary density (vessels per mm²), inflammatory response (0-3 scale) and collagen deposition (0-3 scale) (Table 1).

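### No listed analysis uses baseline wound area or the etiology stratum, so the area-reduction and closure comparisons are valid but less precise than the data already collected would allow.

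*Combined protocol and SAP*

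**What the plan says.** The Materials and Methods section of the combined protocol and SAP admits wounds larger than 20 and smaller than 75 cm², of several types: trauma, surgical dehiscence, burns, pressure ulcers, diabetic foot ulcers and venous leg ulcers.

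Under Outcome Measures: "The primary outcome of the study was percentage wound area reduction", followed from week 1 to week 6 and for one further week. The secondary outcomes include "time to complete wound closure (in days) within 7 weeks, proportion of patients achieving complete closure by week 7", and "Complete wound closure is defined as 100% epithelialization".

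Under Randomization and Blinding: "Randomization was stratified by wound etiology". Wound size is not a stratification factor.

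The Statistical Analysis section lists t-tests or Mann-Whitney tests for continuous variables, chi-square or Fisher tests for categorical ones, and repeated measures ANOVA for longitudinal outcomes. It ends: "Time-to-event outcomes were analyzed using Kaplan-Meier survival analysis with log-rank tests". It names no covariate, regression model or stratified test. Baseline area enters only as the denominator of the percentage.

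**The concern.** Dividing by starting area need not remove the influence of starting area. If a wound closes from its edge, a given advance clears a larger share of a small wound than of a large one. Table 1 itself grades neo-epithelialization by migration from the wound edge. For closure by a fixed week the dependence is more direct, because a larger wound has further to close in the same seven weeks.

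If size predicts outcome and is left out of the analysis, the variation it causes stays in the error term. The confidence interval is then wider than it need be. Baseline area must already be known, both for eligibility and for the percentage, so using it needs no new data. Etiology is in the same position: it was judged important enough to stratify on, but appears in no listed analysis.

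**Working it through.** **Inputs from the documents.** Area range 20 to 75 cm² (ratio 75/20 = 3.75); assumed difference 30 points and SD 20 points; 80% power, alpha 0.05 (two-sided assumed); 47 evaluable and 52 recruited per arm; differences of 10–15% in the cited earlier trials.

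**Not in the documents, so assumed.** Circular wounds; areas uniform on 20–75 cm²; edge advance d of 1 to 2 cm, unrelated to size; the planned SD of 20 taken as the total SD, size included.

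**The plan's own figure.** n = 2 × (20/30)² × (1.960 + 0.842)² = 6.98, or 7 per arm, not 47. At SD 20, 47 per arm fits a difference of 20 × 2.802 × √(2/47) = 11.6 points. That mismatch is a separate matter. It is relevant here only because the value of adjustment depends on which difference is realistic.

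**Step 1: size dependence.** Radius R = √(area/π); reduction = 1 − ((R − d)/R)².

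| Edge advance | 20 cm² | 47.5 cm² | 75 cm² | SD from size alone |
|---|---|---|---|---|
| 1.0 cm | 64% | 45% | 37% | 7.3 points |
| 1.5 cm | 84% | 62% | 52% | 8.8 points |
| 2.0 cm | 96% | 76% | 65% | 8.8 points |

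**Step 2: share of variance.** 7.31²/20² = 13%; 8.77²/20² = 19%. The implied correlations are √0.134 = 0.37 and √0.192 = 0.44 in absolute value.

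**Step 3: standard error.** Unadjusted: 20 × √(2/47) = 4.13 points. Adjusted: multiply by √(1 − 0.134) = 0.931 or √(1 − 0.192) = 0.899, giving 3.84 or 3.71. The reduction is 7 to 10%.

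**Step 4: power.** Normal approximation, Φ(difference/SE − 1.96).

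| True difference | Unadjusted | Adjusted |
|---|---|---|
| 10 points | Φ(0.46) = 68% | Φ(0.64) to Φ(0.74) = 74–77% |
| 15 points | Φ(1.68) = 95% | Φ(1.95) to Φ(2.08) = 97–98% |
| 30 points | above 99.9% | above 99.9% |

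The t distribution lowers the 10-point figures by about one point (67% to 73–76%).

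**Step 5: other correlations.** At 10 points, adjusted power is 68.3% if the correlation is 0.1, 71.9% at 0.3 and 79.9% at 0.5, against 67.9% unadjusted.

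**Step 6: chance imbalance.** Uniform areas have SD 55/√12 = 15.9 cm². One standard error of the difference in mean area at 52 per arm is 15.9 × √(2/52) = 3.1 cm². The fitted slope in Step 1 is about 0.45 to 0.55 points per cm², so such an imbalance moves the estimate by 1.4 to 1.7 points. The unadjusted SE at 52 per arm is 20 × √(2/52) = 3.9 points.

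**Step 7: closure.** To close in seven weeks, a 20 cm² circle (R = 2.52 cm) needs 2.52/7 = 0.36 cm of edge advance per week; a 75 cm² circle (R = 4.89 cm) needs 4.89/7 = 0.70 cm. The dependence is clear under this model. The documents give no closure rate, so I put no power figure on it.

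**The case against.** The strongest reply is that nothing in the plan is in error. Randomization makes the unadjusted comparison valid, and its standard error already allows for chance differences in wound size. That stands. A reader might infer that a size imbalance biases the treatment effect. The documents do not support this: the imbalance is random error, and the 1.4 to 1.7 points in Step 6 is less than half of the 3.9-point SE.

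A reader might also set the 32-point gap between the smallest and largest eligible wounds (84% against 52%) beside the planned SD of 20 and conclude that size swamps the outcome. That compares a range between extremes with a standard deviation. The like-for-like figure is an SD of 7 to 9 points.

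Third, the size-outcome link is assumed. With such mixed wound types, healing rate may vary with etiology or with size, and contraction roughly proportional to size would leave little dependence. This also stands, and it is why the gain is given as a range that reaches almost zero. Etiology strata may balance size in part, but nothing ensures it.

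Finally, repeated measures ANOVA might be thought to use the baseline. The plan names no covariate for it and does not say to which outcomes it applies. Applied to percentage reductions it would contain no baseline area.

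**Conclusion.** The point holds as a loss of precision. The area range, the single stratification factor and the absence of any covariate are read directly from the documents. The size of the loss is conditional: a 7 to 10% larger standard error than necessary, under circular wounds, uniform areas, an edge advance of 1 to 2 cm and a total SD of 20.

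The gain is worth having if the true difference is near the lower end of the 10–15% that the plan itself cites (about 6 to 9 power points at 10), small at 15 points (2 to 3) and nil at 30. A reader might infer that the trial's stated power is at risk. It is not: at the planned 30-point difference power exceeds 99.9% either way. The effect on the closure outcomes is plausible in direction but cannot be sized from the documents.

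**What to change.** - **Primary outcome.** Name the visit (for example week 7). Analyse percentage reduction there by ANCOVA with treatment, log baseline area and etiology. Define baseline area as the last measurement before the first study treatment, since the outcome wording starts at week 1.
- **Closure.** Add a Cox model for time to closure and logistic regression for closure by week 7, with the same covariates. Give estimates with 95% confidence intervals beside the Kaplan-Meier curves. State that the adjusted hazard and odds ratios are conditional effects, which generally differ from the unadjusted ones even without imbalance.
- **Sparse etiologies.** Six wound types are listed, so fix in advance how small categories will be pooled.
- **Unadjusted tests.** Report them alongside.
- **Timing.** The document is dated November 2025, is written in the past tense and anticipates follow-up to August 2025. It does not say whether unblinded data had been seen. If they have, keep the stated tests as the main analysis and label the adjusted models as sensitivity analyses. If not, date the change and record that it was made blind.

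The cost is wording in the analysis section and a few lines of code in the software already named. No new data or patients are needed.

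### As written, pain change would be compared without adjusting for baseline VAS, a comparison that in large samples is never more precise than ANCOVA

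*Combined protocol and SAP*

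**What the plan says.** Outcome Measures lists, among the secondary outcomes, the change in pain on a 0–10 "Visual Analog Scale (VAS) from baseline to week 6". Data Collection and Measurement says "Pain assessments (Visual Analogue Scale) and quality of life score were completed at baseline, every week thereafter for 7 weeks", so a baseline score exists for use as a covariate.

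Statistical Analysis is generic. Continuous variables are "compared using independent t-tests or Mann–Whitney U tests where appropriate", and "Repeated measures ANOVA was employed for longitudinal outcome analysis". It does not say which of these applies to pain or how baseline enters, and it names no ANCOVA, covariate or other adjusted model.

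The Introduction's hypothesis includes "better patient-reported pain outcomes" among four expected benefits. Under Randomization and Blinding, allocation is 1:1 and stratified by wound etiology.

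**The concern.** A change score subtracts the whole baseline value, whatever the true relation between baseline and week-6 pain. If that relation is weaker than one-for-one, the subtraction adds baseline noise to the comparison, and part of any chance difference in baseline pain carries through to the estimated treatment effect. Adjustment for baseline estimates the relation from the data and removes only what baseline predicts.

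At stake is the precision of one of the four benefits named in the hypothesis. The confidence interval could be wider than the collected data require, and an effect on pain could be missed for that reason alone.

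**Working it through.** **Inputs.** The endpoint, schedule, test list and allocation ratio are as described above. The sample sizes, 47 per group and 52 after the dropout allowance, come from the Sample Size paragraph. They were set for wound area, and whether they follow from their own inputs is a separate question. The plan gives no sample size, power, SD or correlation for pain, so there is no plan figure to reproduce.

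**Step 1: what the text leads to.** A two-sample test of the defined endpoint is an unadjusted comparison of changes. In a repeated measures ANOVA with baseline as a time level, the group-by-time contrast from baseline to week 6 is the same difference in mean change. If baseline is left out of the time levels, it is not used at all. No route in the text adjusts for it.

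**Step 2: variances.** Let r be the correlation of baseline with week-6 VAS and k = SD_week6/SD_baseline. In units of the week-6 variance, the large-sample variance of the treatment difference is proportional to:

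- week-6 score alone: 1
- change score: (1 + k² − 2rk)/k²
- ANCOVA: 1 − r²

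Change minus ANCOVA is (1 + k² − 2rk − k² + r²k²)/k² = (1 − rk)²/k². This is never negative, and it is zero only when rk = 1, where rk is the slope of week-6 on baseline VAS. These formulas are for comparisons of means; they are not exact for Mann-Whitney U.

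**Step 3: equal SDs (k = 1, assumed).** Change is 2(1 − r), so ANCOVA/change is (1 − r²)/[2(1 − r)] = (1 + r)/2.

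| r | ANCOVA/change variance | Fall in standard error | Change/week-6-alone variance |
|---|---|---|---|
| 0.2 | 0.60 | 23% | 1.60 |
| 0.3 | 0.65 | 19% | 1.40 |
| 0.5 | 0.75 | 13% | 1.00 |
| 0.7 | 0.85 | 8% | 0.60 |
| 0.9 | 0.95 | 3% | 0.20 |

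The fall in standard error is 1 − √[(1 + r)/2]. The last column shows that the change score is noisier than the week-6 score alone when r < 0.5.

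**Step 4: power.** Take 47 per group, two-sided alpha 0.05 (sidedness is not stated), equal SDs, and an effect giving 80% power for the week-6 score alone. Power for change versus ANCOVA is then 66% versus 84% at r = 0.3, 80% versus 90% at r = 0.5, and 95% versus 98% at r = 0.7.

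**Step 5: unequal SDs.** The change score is noisier than the week-6 score alone when r < 1/(2k), that is, r < SD_baseline/(2 × SD_week6). The cut-off is 0.71 at k = 0.7 and 0.40 at k = 1.25. At r = 0.3 the change/ANCOVA variance ratio is 2.184/0.91 = 2.40 for k = 0.7 and 1.16/0.91 = 1.27 for k = 1.25. At k = 1.5 and r = 0.7, where the slope is near 1, it is 1.002.

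**Step 6: finite samples.** Estimating the slope costs ANCOVA a factor of about 1 + 1/(2n − 4), which is 1 + 1/90 = 1.011 at n = 47 per group. A simulation at that size (5,000 runs per setting) gave change/ANCOVA ratios of 1.49 at r = 0.3 and 1.30 at r = 0.5 with equal SDs, against 1.54 and 1.33 from the formula. With k = 1.25 and r = 0.8 (slope 1) it gave 0.991.

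**Step 7: chance imbalance.** With an assumed SD of 2 points and 52 per arm, one standard error of the baseline difference is 2 × √(2/52) = 0.39 points. With equal SDs and r = 0.3, an imbalance of that size shifts the expected change-score estimate by (1 − 0.3) × 0.39 = 0.27 points. ANCOVA removes this shift.

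**The case against.** The strongest reply is that no test is assigned to pain. The scores are weekly, so repeated measures ANOVA is an obvious candidate, and a change endpoint is itself compatible with adjustment: linear ANCOVA of change on baseline gives the same treatment estimate as ANCOVA of week-6 VAS. A reader might infer that the plan commits pain to an unadjusted t-test. The documents do not say so. What stands against the reply is that no listed method, as described, includes a baseline covariate (Step 1).

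A reader might also infer that the change score is always less precise, or that 0.5 is a general cut-off. Neither holds. The two methods tie when the slope is 1, where ANCOVA is about 1% worse at this sample size, and the 0.5 figure needs equal SDs. Equal SDs are doubtful when healed and unhealed wounds are mixed at week 6. Unequal SDs can make the loss larger or smaller.

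Nor can the correlation be presumed low. Stable pain differences between etiologies would tend to raise it, and at r = 0.9 with equal SDs the variance saving is only 5%.

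Finally, this is one secondary outcome. The primary outcome and the type I error rate are unaffected.

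**Conclusion.** The point holds as one of efficiency. Following the text gives an unadjusted comparison of pain change, which in large samples cannot be more precise than ANCOVA and equals it only at a slope of 1. With equal SDs, adjustment would cut the variance by 40% at r = 0.2 and by 5% at r = 0.9. The documents do not fix where in that range the trial lies, or whether equal SDs are reasonable.

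A reader might infer that the planned estimate is biased. Under 1:1 randomisation it is not: averaged over repeated randomisations the change-score comparison is unbiased. What remains is error conditional on a chance baseline imbalance. The 0.27-point illustration of that error rests on an assumed SD of 2 and r = 0.3.

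The change should be made because the gain is likely to exceed its very small cost, but it does not put the trial's main conclusion in doubt.

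**What to change.** State one method for pain: ANCOVA of week-6 VAS with treatment, baseline VAS and the stratification factor, wound etiology. Alternatively, use a mixed model for the weekly scores with the same covariates and the week-6 contrast as the target. Report the adjusted mean difference with its 95% CI, and keep change from baseline as description.

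Do the same for the EQ-5D index and EQ-VAS, which also have a baseline. Do not extend linear ANCOVA to the day-5 histology grades scored 0–3: these are four-level ordinal scores, for which a linear model is a doubtful default.

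The cost is a little more analysis work, about 1% in variance if the slope is near 1, and the degrees of freedom used for etiology. No new data are needed.

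Timing needs care. The document is dated November 2025, recruitment ended in July 2025, follow-up was expected to end in August 2025, and the analysis is described in the past tense. If outcome data have already been seen, label the adjusted analysis as post hoc or as a sensitivity analysis alongside the unadjusted one.
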